#### 4.2. Treatment Arms and Duration

This study consists of a Screening phase (within 28 days period before first treatment), a Treatment phase 1 (double-blind treatment phase: 12 to 48 weeks period after first treatment), and a Treatment phase 2 (open-label treatment phase: 12 to 36 weeks period after first treatment). The duration of overall treatment phase is 48 weeks.

Following the Screening phase, patients meeting the eligibility criteria will be randomly assigned by the registration center to one of the 2 treatment arms (either 100 U GSK1358820 or placebo) in a ratio of 1:1. Subsequently, in Treatment phase 1, patients will receive single treatment with the allocated study drug (20 injections each of 0.5 mL) which will be injected into the detrusor of the bladder. At the randomization, patients will be stratified according to the number of urinary urgency incontinence episodes reported prior to initiation of treatment phase 1 (Week 0),  $\leq 9$  or  $\geq 10$  episodes, over the consecutive 3-day diary completed during the screening phase.

Subjects who meet the criteria for re-treatment (referred to the section 5.3 Re-treatment criteria) between 12 to 36 weeks after 1st treatment can enter to Treatment phase 2 to receive re-treatment (GSK1358820 100 U). Patients are permitted to receive re-treatment until up to 36 weeks after 1st treatment and at most 2 times (Note: a minimum of 12 weeks need to be elapsed since previous study treatment). Subjects who did not receive re-treatment will remain in Treatment phase 1 and continue to visit at the scheduled study visits. Patients who complete the evaluation at 48 weeks after 1st treatment are regarded as the patients who complete the study, regardless of whether the subject was re-treated or not.

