Urinary retention	
As the result of integrated data with 1 completed phase 2 study (191622-077), 2 completed pivotal phase3 study (191622-095 and 191622-520) and an interim cut of the long-term extension study (191622-096), the frequency of urinary retention as an adverse event occurred in 7.1% of patients in the 100 U BOTOX group and 0.5% of patients in the placebo group (refer to IB section 5.2.4.2 Overactive Bladder).
 
Intradetrusor injection of BOTOX causes a detrusor muscle relaxation that leads to a decrease in the contractions of the detrusor muscle. This detrusor muscle relaxation may lead to an inability of the detrusor muscle to effectively contract during voiding in some patients thus causing a residual accumulation of urine in the bladder evident as an increased PVR volume, or may manifest as a patient's inability to void due to urinary retention (refer to IB section 5.2.5 Clinical Safety in the published literature ).
	
Patients with potential risk for these events will be excluded from this study (refer to Protocol section 5.2 exclusion criteria 22, 23 and 26 )
 
PVR urine volume will be assessed at each visit. Clean intermittent catheterization (CIC) and additional follow-up visit will be performed dependent on the PVR as well as subject's symptoms (refer to Protocol section 7.4.7.Post-void residual urine volume and Appendix 5 Management guideline of PVR).

Pyelonephritis	
In OAB clinical studies, pyelonephritis as an AE was also very uncommon and was reported as a non-serious adverse event in one patient during placebo-controlled treatment cycle 1. However, based on the patient population who will be receiving instrumentation to deliver intradetrusor injections of BOTOX, and a potential temporary increase in PVR urine post treatment, mainly in
	
Please refer to the mitigation strategy UTIs.

	the first 12 weeks, patients with bladder disorders with urinary incontinence who have a prior UTI may potentially progress from UTI to pyelonephritis.	
Other		

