The total volume voided will be measured and recorded by subjects over one 24-hour period during the 3-day bladder diary collection period (urine volume of urinary incontinence will not be measured and recorded). To perform this measurement, urine collection containers provided by the sponsor will be used. The volume voided per micturitionb will be determined by the sponsor from the total urine volume measured by the subjects divided by the number of micturitions (excluding urinary incontinence episode).

If a subject has symptoms of a urinary tract infection, the diary data will not be collected during this period because the data may have influence on the bladder diary data.

a: used for evaluation of primary endpoint (Change from baseline in the daily average number of urinary incontinence episodes a at week 12 after the first treatment)

b: used for evaluation of major secondary endpoint (Change from baseline in the average volume voided per micturition at week 12 after the first treatment)

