#### Initiation of CIC

CIC should only be initiated when one of the following criteria is fulfilled:

- PVR is  $\geq 350 \text{ mL}$  at any post treatment visit, regardless of reports of associated symptoms by subjects; or
- PVR is  $\geq 200 \text{ mL}$  and  $< 350 \text{ mL}$  and the subject spontaneously reports associated symptoms (e.g., voiding difficulties and sensation of bladder fullness) that in the opinion of the investigators/subinvestigators require CIC.

The following will occur when initiating CIC:

- 1) CIC should be performed using sterile, single-use catheters.
- 2) An adverse event of urinary retention should be recorded.
- 3) A urine analysis with a urine reagent strip as well as urinalysis, urine culture and sensitivity test at the central laboratory should be performed. In addition, these tests and analyses will be performed at scheduled visits after CIC is initiated.
- 4) The subject should be seen at a follow-up visit 1 week later, when the results of PVR measurement, associated symptoms, and a urine analysis with a urine reagent strip are

reassessed while urinalysis, urine culture and sensitivity test are performed for reassessment at the central laboratory. The investigators/subinvestigators will determine whether the subject should then be followed at regularly scheduled study visits or whether additional visits should occur.

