## 9.2. Sample Size Considerations

### 9.2.1. Sample Size Assumptions

The sample size for this study is hypothesized based on the observed treatment difference in the change from baseline of the daily average number of urinary incontinence episodes and the average volume voided per micturition at Week 12 from the integrated data of studies 191622-095/191622-520. It is assumed that the mean differences in the daily average number of urinary incontinence episodes and the average volume voided per micturition between GSK1358820 and placebo are -1.79 episodes/day and 30 mL from these studies results. Using the two sample t-test, 240 subjects in total (120 subjects for each treatment group) is required to achieve at least 89% power at the two-sided significance level of 5% to detect the assumed treatment differences for the daily average number of urinary incontinence episodes and the average volume voided per micturition simultaneously when common standard deviations (SD) are 3.5 episodes/day in the daily average number of urinary incontinence episodes and 70 mL in the average volume voided per micturition. This power is calculated by using power of each endpoint and Bonferroni inequality. Using above assumed values, power is 98% for the daily average number of urinary incontinence episodes and 91% for the average volume voided per micturition at the two-sided significance level of 5%. In this case, joint power is expected at least 89% (=98 + 91 -100) calculated by Bonferroni inequality.

The minimum detectable effect (i.e., the smallest observed effect size that could be statistically significant) based on the two sample t-test is a -0.9 episodes/day in the daily average number of urinary incontinence episodes and a 17.8mL in the average volume voided per micturition, respectively, when common standard deviations are 3.5 episodes/day in the daily average number of urinary incontinence episodes and 70 mL in the average volume voided per micturition.

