Daily average number of voids	Number of "Yes" response to the diary question of "Did you urinate into the toilet?"	
Daily average number of urgency episodes	Number of "Yes" response to the diary question of "Was this episode associated with a sudden and urgent need to urinate?"	
Daily average number of nocturia episodes (voids that	Number of "Yes" response to the diary question of "Did this	

Diary Data Convention		
interrupt night sleep)	episode wake you from night sleep?"	
Daily average number of severe urgency episodes	Number of "3-Severe Urgency" response to the diary question of "How would you rate your need to urinate?"	
Daily average number of severe or moderate urgency episodes	Number of "3-Severe Urgency" or "2-Moderate Urgency" response to the diary question of "How would you rate your need to urinate?"	
Average volume voided per micturition	The total volume collected in 24-hour period	Number of the urinary volume records which are not missing

 For the endpoint of Proportion of patients attaining 100%, $\geq 75\%$ and $\geq 50\%$ reduction from baseline in the daily average of urinary (urgency) incontinence episodes, if change from baseline in the daily average of urinary (urgency) incontinence episodes 
 is -100%, then this subject will attain 100%, $\geq 75\%$ and $\geq 50\%$ falls the range (-100 < , $\leq -75\%$), then this subject will attain $\geq 75\%$ and $\geq 50\%$ falls the range (-75 < , $\leq -50\%$), then this subject will attain $\geq 50\%$ is larger than -50%, then this subject will not attain any category 		

 For Proportion of subjects with maximum urgency intensity and Change from baseline of maximum urgency intensity, "maximum" will be defined as the maximum urgency intensity within 3-day period (but only for valid diary day) in the visit. This will be derived as one record per one visit. 		
Handling of partial missing data in diary (except for urinary time)		

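### The SAP does not limit average volume voided per micturition to spontaneous voids, so any catheter volume entered in the diary would count as voided volume, mainly on active; the likely size is small.

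*SAP*

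**What the plan says.** SAP 11.6.3 (both SAP versions in the file) takes "The total volume collected in 24-hour period" as the numerator and "Number of the urinary volume records which are not missing" as the denominator. In the same table, the daily number of voids counts only episodes for which the subject answered that they urinated into the toilet. The volume row has no such filter. The rules for partly missing diary data, later in the same section, show that the volume item is asked for each episode and allows an entry that nothing was collected.

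Protocol 7.3.1.1 describes micturitions as toilet voids, as does inclusion criterion 4. It lists CIC use among the diary contents and leaves out one source of urine by name: "urine volume of urinary incontinence will not be measured and recorded". It does not mention catheterised urine. It divides total volume by the number of micturitions, whereas the SAP divides by the number of volume records.

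On catheter use by arm, Protocol 4.6.1 gives urinary retention in earlier studies as "7.1% of patients in the 100 U BOTOX group and 0.5% of patients in the placebo group". Under Protocol 7.4.7, a retention adverse event is recorded in this trial only when CIC is required. CIC starts at a post-void residual of 350 mL or more, or at 200 to below 350 mL with symptoms judged to need it.

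**The concern.** The endpoint is meant to show that the bladder stores more urine and that the subject passes more at each void. A catheter record measures urine that the subject did not pass. Under the SAP formula such a record adds its volume to the numerator and one to the denominator. The subject's average then rises if the catheter volume exceeds that subject's usual void. An unwanted effect of the drug could then be scored as benefit, mostly in one arm.

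The endpoint carries weight. Protocol 9.2.1 sizes the trial on it jointly with the primary endpoint, and SAP 5.5 says that both hypotheses have to be confirmed. No other section closes the gap:

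- The intercurrent-event table in SAP 7.1.4, applied to this endpoint by 7.2.4, does not list catheter use.
- The per-protocol exclusions in Appendix 1 do not mention it.
- The CIC rules in SAP 8.5 and Appendix 12 serve the safety displays only.

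**Working it through.** **The plan's own figures.** Protocol 9.2.1 gives 120 subjects per arm, a 30 mL difference, an SD of 70 mL and a two-sided 5% level.

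- Standard error: 70 × √(2/120) = 9.04 mL.
- Power: Φ(30/9.04 − 1.96) = Φ(1.36) = 0.913, stated as 91%.
- Smallest significant difference: t(0.975, 238 df) × 9.04 = 17.8 mL, as stated.

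Both reproduce and are not in dispute.

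**Rise in one affected subject under the SAP rule.** Let 9 voids have mean v mL, and let n catheterisations of c mL be entered as volumes on the collection day. The documents give none of these values; all are assumptions. The catheter volumes of 200 and 350 mL are borrowed from the CIC starting thresholds.

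Rise = (9v + nc)/(9 + n) − v = n(c − v)/(9 + n)

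| v (mL) | n | c (mL) | Rise (mL) |
|---|---|---|---|
| 100 | 1 | 200 | 10.0 |
| 100 | 1 | 350 | 25.0 |
| 100 | 3 | 200 | 25.0 |
| 100 | 3 | 350 | 62.5 |
| 150 | 1 | 200 | 5.0 |
| 150 | 1 | 350 | 20.0 |
| 150 | 3 | 200 | 12.5 |
| 150 | 3 | 350 | 50.0 |

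**Shift in the active-arm mean** = share of the arm on CIC that day × rise.

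- At 2% (2.4 of 120 subjects): 0.02 × 5 = 0.1 mL to 0.02 × 62.5 = 1.25 mL, at most 4% of 30 mL.
- At 7%: 0.07 × 5 = 0.35 mL to 0.07 × 62.5 = 4.4 mL, at most 15% of 30 mL.

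**Direction.** The rise has the sign of c − v. With v = 150, c = 100 and n = 3 it is 3 × (−50)/12 = −12.5 mL, so the bias is upward only when catheter volumes are larger than usual voids.

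**A wider check with heavier catheter use.** Let f be the share of retention patients still catheterising on the Week 12 collection day, and s the rise per patient. The shift in the arm difference is (7.1% − 0.5%) × f × s. With f = 0.25 (about 2.1 active patients) and s = 100 to 200 mL, it is 0.066 × 0.25 × 100 = 1.65 mL to 3.3 mL. With no true effect, the two-sided rejection rate would be 5.4% to 6.4% instead of 5%. A rise near 100 mL needs a pattern such as 6 voids of 120 mL and 4 catheterisations of 350 mL: (720 + 1400)/10 = 212, a rise of 92 mL.

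**The case against.** The strongest reply is that the mechanism is not shown to operate. Diary instructions are in the study reference manual and on the diary itself, neither of which is in the file. The protocol speaks of volume voided and of toilet voids, and drained urine is neither. A subject could also mark a catheter episode as not collected. This stands as a limit: the shift may be zero. It does not remove the gap, because the SAP formula that will be programmed does not carry the protocol's restriction.

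It can also be said that affected values could be found in the planned listings of raw diary, derived diary and CIC data. That is true, but a listing does not say how the value should be derived.

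A reader might draw four stronger conclusions that the documents do not support:

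- **That 7% of the active arm will be catheterising on the day.** The 7.1% is the share with retention as an adverse event in pooled earlier studies, including an extension. The endpoint uses one 24-hour collection. Protocol 4.6.1, in the pyelonephritis row, expects any residual-volume increase to be temporary and mainly within the first 12 weeks. Taking f = 1 and s = 200 mL would give 13.2 mL, but this needs every such patient to be still catheterising, with a rise over three times the largest in the table.
- **That the error can only favour active.** Volumes during established CIC may be smaller than those at its start.
- **That the protocol's formula makes the inflation worse.** This requires catheter urine in the numerator but not in the count. The protocol's numerator refers back to volume voided, and the SAP derivation is the planned analysis.
- **That the incontinence analysis needs a run with on-CIC diaries set to baseline.** No catheter-volume error arises in that endpoint, and the substitution is a debatable choice of estimand.

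**Conclusion.** The gap is real and should be closed. As written, the formula departs from the protocol's meaning of volume voided per micturition, and catheter use is expected mainly on active. The likely effect is small: about 0.1 to 1.3 mL on the active-arm mean at 2% on CIC, with an extreme case of about 4.4 mL at 7%, against a planned 30 mL. The wider check, with heavier catheter use, gives 1.65 to 3.3 mL on the arm difference. All these figures rest on assumed void sizes, catheter volumes and CIC prevalence at Week 12, and on catheter volumes being entered at all. Weeks 2 and 6 could be affected more than Week 12. This is a rule to fix in advance and does not by itself put the endpoint's result in doubt.

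**What to change.** Before unblinding, amend SAP 11.6.3 for this endpoint:

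- Let only toilet-void volumes enter both the numerator and the record count. These are episodes for which the subject answered that they urinated into the toilet, and whose urine was not obtained by CIC or indwelling catheter.
- Identify catheter volumes from the diary's CIC item, or from the CIC start and stop dates in the CRF. The protocol lists the diary item without saying whether it is recorded per episode, so check the diary layout first.
- Treat the visit value as missing if no spontaneous void volume remains. The existing MMRM and controlled-imputation rules then apply.
- Reconcile the denominator with Protocol 7.3.1.1, which counts micturitions where the SAP counts volume records.

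The cost is SAP wording and a line of programming on data already collected. The downside is that a few CIC users' averages rest on fewer records or become missing. If no catheter volumes were entered, limiting the records to spontaneous voids changes nothing on this account. The change concerns the derivation only and leaves the management of catheterisation as it is.

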7.3.1. Endpoint / Variables

- Changes from baseline and percentage change from baseline in the following endpoints
 - Daily average number of urinary incontinence episodes
 - Daily average number of urinary urgency incontinence episodes
 - Daily average number of voids
 - Average volume voided per micturition
 - Daily average number of urgency episodes
 - Daily average number of nocturia episodes (voids that interrupt night sleep)
- Urgency intensity
 - Change from baseline in daily average number of urgency episodes by each urgency intensity category
 - Proportions of patients with maximum urgency intensity
 - Change from baseline of maximum urgency intensity
- Proportion of patients attaining 100%, $\geq 75\%$ and $\geq 50\%$ reduction from baseline in the daily average of urinary incontinence episodes
- Proportion of patients attaining 100%, $\geq 75\%$ and $\geq 50\%$ reduction from baseline in the daily average of urinary urgency incontinence episodes
- Duration of treatment effect after 1st treatment
 - Time to qualification for retreatment
 - Time to request for retreatment
- Health outcome
 - Changes from baseline in King's Health Questionnaire (KHQ) domain scores
 - Proportion of patients with positive response on the Treatment Benefit Scale (TBS)
 - Changes from baseline in Overactive Bladder Symptom Score (OABSS) total score

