General Health Perception	1 (1 item)		1= Very Good 2= Good 3= Fair 4= Poor 5= Very Poor	Domain Score = $(\text{score of left item} - 1) / 4 * 100$
Incontinence Impact	2 (1item)		1= Not at all 2= A little 3= Moderately 4= A lot	Domain Score = $(\text{score of left item} - 1) / 3 * 100$
Role Limitations	3a and 3b (2 items)		1= Not at all 2=Slightly 3=Moderately 4=A lot	Domain Score = $(\text{summed scores of left items} - 2) / 6 * 100$
Physical Limitations	4a and 4b (2 items)		1= Not at all 2=Slightly 3=Moderately 4=A lot	Domain Score = $(\text{summed scores of left items} - 2) / 6 * 100$
Social Limitations	4c, 4d, 5c (3 items)		0= N/A 1= Not at all 2=Slightly 3=Moderately	Domain Score = $(\text{summed scores of left items} - 3) / 9 * 100$ If score of 5c = 0 then

KHQ and OABSS Convention				
Derivation of KHQ domains				
			4=A lot	Domain Score = (summed scores of left items -2) / 6 * 100
Personal Relationships	5a and 5b (2 items)		0= N/A 1= Not at all 2=Slightly 3=Moderately 4=A lot	Domain Score = (summed scores of left items -2) / 6 * 100 If summed scores of left items = 1 then Domain Score = (summed scores of left items -1) / 3 * 100 If summed scores of left items = 0 then Domain Score will be treated as missing
Emotions	6a, 6b and 6c (3 items)		1= Not at all 2=Slightly 3=Moderately 4=Very Much	Domain Score = (summed scores of left items -3) / 9 * 100
Sleep/Energy	7a and 7b (2 items)		1= Never 2=Sometimes 3=Often 4=All the time	Domain Score = (summed scores of left items -2) / 6 * 100
Severity/Coping Measures	8a, 8b, 8c, 8d and 8e (5 items)		1= Never 2=Sometimes 3=Often 4=All the time	Domain Score = (summed scores of left items -5) / 15 * 100
Derivation of OABSS total score				
OABSS total score will be calculated as the sum of scores for following questions [Homma, 2006].				
Question	Answer (Frequency)		Score	
How many times do you typically urinate from waking in the morning until sleeping at night?	≤ 7		0	
	8-14		1	
	≥ 15		2	
How many times do you typically wake up to urinate from sleeping at night until waking in the morning?	0		0	
	1		1	
	2		2	
	≥ 3		3	
How often do you have a sudden desire to urinate, which is difficult to defer?	Not at all		0	
	Less than once a week		1	

CONFIDENTIAL

204947

KHQ and OABSS Convention		
Derivation of KHQ domains		
	Once a week or more	2
	About once a day	3
	2-4 times a day	4
	5 times a day or more	5
How often do you leak urine because you cannot defer the sudden desire to urinate?	Not at all	0

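### The KHQ Personal Relationships rule as written cannot rescale a single answered item, so a subject with exactly one N/A item can score at most 33.3 out of 100; only descriptive summaries are affected.

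*SAP*

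**What the plan says.** SAP 11.6.3, under the KHQ and OABSS conventions, defines the Personal Relationships domain on "5a and 5b (2 items"), with the response scale "0= N/A 1= Not at all 2=Slightly 3=Moderately" and 4 for the worst answer. Three rules follow.

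- Default: subtract 2 from the sum of the two items, divide by 6 and multiply by 100.
- "If summed scores of left items = 1 then" the score is ("summed scores of left items -1) / 3 * 100".
- "If summed scores of left items = 0 then" the domain is set to missing.

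The row reads the same in both versions of the analysis plan contained in the SAP. The row above it, Social Limitations, handles N/A by looking at the item: "If score of 5c = 0 then" the formula changes to one for the two remaining items.

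SAP 7.3.1 lists "Changes from baseline in King's Health Questionnaire (KHQ) domain scores" among the other secondary endpoints. SAP 11.6.3, SAP 7.3.5.1 and the programming note to Table 2.93 restrict the ANCOVA to Role Limitations and Social Limitations. The other domains are only summarised.

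**The concern.** The second formula maps one item scored 1 to 4 onto 0 to 100, so it is evidently meant for a subject who answered one item and marked the other N/A. Such a subject has a sum of 1, 2, 3 or 4, depending on the answer. The condition catches only the first of these. For the rest, one answer is scored as if it were the sum of two, and the result is too low, which means too healthy.

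At stake is the accuracy of a reported secondary endpoint. If a subject's N/A status changes between visits, part of the change from baseline comes from the scoring rule. If one item is N/A throughout, real change is shrunk.

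**Working it through.** The plan states no figure on this point, so the check is to enumerate the rule.

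**Inputs**, all from SAP 11.6.3: items 5a and 5b; codes 0 (N/A) and 1 to 4; default formula (sum − 2)/6 × 100; one-item formula (sum − 1)/3 × 100, used at sum = 1; missing at sum = 0.

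**Step 1: the one-item formula under its own condition.** At sum = 1 it gives (1 − 1)/3 × 100 = 0. The division by 3 never has any effect.

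**Step 2: exactly one item N/A.** The sum equals the answered item.

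| Answered item | SAP as written | Answered item rescaled | Understatement |
|---|---|---|---|
| 1 | (1 − 1)/3 × 100 = 0 | (1 − 1)/3 × 100 = 0 | 0 |
| 2 | (2 − 2)/6 × 100 = 0 | (2 − 1)/3 × 100 = 33.3 | 33.3 |
| 3 | (3 − 2)/6 × 100 = 16.7 | (3 − 1)/3 × 100 = 66.7 | 50.0 |
| 4 | (4 − 2)/6 × 100 = 33.3 | (4 − 1)/3 × 100 = 100 | 66.7 |

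The score spans 0 to 33.3 instead of 0 to 100. An answer of 2 with one N/A item scores 0, the same as an answer of 1 on both items.

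**Step 3: all other pairs.** With both items answered, or both N/A, the SAP rule and an item-level rule agree for every combination.

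**Step 4: does another rule catch these subjects?** SAP 11.6.3 sets a KHQ item or domain to missing when data are missing. SAP 11.7.2 says that an answer of not applicable does not count as missing. The N/A item therefore stays in as 0.

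**Step 5: the neighbouring row.** In Social Limitations with 5c = 0, items 4c and 4d sum to between 2 and 8. The score runs from (2 − 2)/6 × 100 = 0 to (8 − 2)/6 × 100 = 100, so the full scale is kept.

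**Step 6: change from baseline.**
- N/A status changes: both items at 4 give 100 at baseline. One item N/A and the other still 4 gives 33.3 later, an apparent improvement of 66.7 points. Rescaling the answered item gives 100 at both visits. The reverse sequence gives a false worsening.
- N/A status stable: a fall from 4 to 1 on the answered item shows as 33.3 points instead of 100. A fall from 2 to 1 shows as 0 instead of 33.3.

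**Step 7: group means.** If a share f of the scored subjects in an arm at a visit has exactly one N/A item, the mean score is too low by at most 66.7 × f. The documents give no value for f.

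**The case against.** The strongest objection concerns authority. The SAP does not present this table as its own design. SAP 11.6.3 attributes it to a cited 2015 clinical guideline. Protocol 7.3.1.2.1 says that scores follow the questionnaire developer's algorithm, and protocol Appendix 3 (12.3.4) requires the developer's standard scoring for outcome questionnaires. None of these sources is available here. A reader might infer that the sponsor mistranscribed the condition. The documents cannot show that: it may be the source's own wording, in which case an unconditional replacement would depart from the protocol. This stands, and it makes the remedy conditional. It does not repair the arithmetic, because the one-item formula has no effect wherever the condition came from.

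The second objection concerns impact. A reader might infer that KHQ results could be off by 67 points, or that a treatment comparison is distorted. Neither follows. The 66.7 is a worst case for one subject at one visit. It needs exactly one N/A item and the most severe answer on the other. How often one item is N/A is not stated, and nothing in the documents suggests that it differs by arm. Under the SAP the domain has no model, treatment contrast or p-value. Protocol 9.4.2 does name KHQ domain scores for ANCOVA without limiting the domains, so this limit on impact rests on the SAP, the more specific document.

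Third, the Social Limitations row is an imperfect comparator. It shows N/A in the scale of a three-item domain but tests only 5c, and it does not say which items permit N/A. It shows that an item-level test is used elsewhere in the same table, not what the Personal Relationships algorithm must be.

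**Conclusion.** The point holds in this form. Read literally, the rule underscores any subject with exactly one of 5a and 5b N/A and the other answered 2, 3 or 4, by 33.3, 50.0 or 66.7 points, and caps such subjects at 33.3. All other response patterns are scored consistently.

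The affected outputs are the descriptive KHQ summaries: Tables 2.91 and 2.92 for the first treatment cycle, and 2.94 to 2.97 for the second and third. The primary endpoint, the major secondary endpoint and every planned p-value are untouched. The effect on group means cannot be quantified.

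The conclusion rests on two assumptions: that N/A is stored as 0 and summed, as the SAP's coding and its missing-data rules say, and that a single answered item should be rescaled to 0 to 100, as the SAP's own one-item formula does.

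**What to change.** Check the condition against the guideline cited in SAP 11.6.3 and the developer's algorithm that the protocol points to.

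- **If the source does not require a sum of 1**, replace the rule. When exactly one of 5a and 5b is 0, the score is (answered item − 1)/3 × 100. When both are 0, the domain is missing. Otherwise it is (sum − 2)/6 × 100.
- **If the source does require it**, keep the standard score and say so in the SAP. Add a supplementary summary using the item-level rule, and report by arm and visit the number of subjects with exactly one N/A item.

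The replacement costs one line of SAP wording and one derivation statement. The second route adds one summary and one count. Neither changes any score where both items are answered or both are N/A.
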